3.3. Objectives and Hypotheses

3.3.1. Primary Hypotheses and Objective

To determine whether the provision of a service that delivers smartphone-assisted PST specifically designed for men who present to the Emergency Department with self-harm, results in fewer suicides and/or contacts with Emergency Departments for self-harm, compared with usual care, in the year after the index episode.

We anticipate that in sites implementing a service that delivers smartphone-assisted PST specifically designed for men, 12 months after the index episode, there will be:

- 1. Fewer deaths by suicide; and/or
- 2. Fewer contacts with the Emergency Departments in Ontario for the repetition of self-harm.

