3.3.2. Secondary Hypotheses and Objectives

The key secondary objectives are to determine, compared to usual care, whether the provision of a service that delivers smartphone-assisted PST specifically designed for men who present to the Emergency Department with self-harm, results in:

- 1. Lower suicide rates;
- 2. Fewer contacts with any Emergency Departments in Ontario for the repetition of self-harm;
- 3. Fewer contacts with any Emergency Department in Ontario for any reason;
- 4. Fewer admissions to hospital for any reason;
- 5. Fewer outpatient appointments for any reason at any hospital in Ontario;
- 6. Lower mortality rates, not related to suicide;
- 7. Lower use of primary care services (defined by contact with a family physician); and/or
- 8. Decreased costs to the health care system, including physician, hospitalization, Emergency Department, and other costs.

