4.1.2. Eligibility Criteria

Sites were deemed eligible if they averaged at least 50 self-harm presentations by men per year. and an absolute re-presentation rate of at least 6 over three years. This resulted in a list of 25 eligible Emergency Departments in Ontario. Eligible patients will be identified in ICES, using the following criteria:

Incl	usion Criteria
1	Patient has presented with an index episode of intentional self-harm at an eligible
1.	Emergency Department in Ontario, Canada.
2.	Patient is biologically male.
3.	Patient is 18 years of age or older.
4.	Patient has a valid OHIP number.
Exc	lusion Criteria
1	Patient has presented to the Emergency Department for a reason other than intentional
1.	self-harm at an eligible Emergency Department in Ontario, Canada.
2.	Patient is biologically female.
3.	Patient is under 18 years of age.
4.	Patient does not have a valid OHIP number.

Intentional self-harm is defined as intentional self-poisoning or self-injury, whether or not there is evidence that the act was intended to result in death. This will be identified using ICD-10-CM codes T14.91, X71-X83 ICD-10 codes from health administrative databases held at ICES.

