4.1.4. Outcomes

The primary outcome measure will be a composite of the incidence of suicides and/or re-presentations to any Emergency Department in Ontario for self-harm in the year after the index episode of self-harm. The incidence of suicide and re-representation to Emergency Department will be measured using ICD-10-CM codes T360-T50992, T510-T6592, T71112-T71232, X71-X83 (refer to Appendix A for full list of codes and descriptors) [46]. Individuals who died by suicide will be identified in ICES using the Vital Statistics - Death Database. A potential problem with the outcome measures in this trial is that the intervention may also change help-seeking behaviour. That is, men may seek out healthcare that they would not have in the past, which may lead to an increase in re-presentations to the Emergency Department for patients in the intervention group. In order to explore changes to health-related help-seeking, we will also collect data on primary care and hospital outpatient care not driven by emergencies through ICES. This will be measured in ICES, using the Ontario Health Insurance Plan (OHIP) Claims Database and National Ambulatory Care Reporting System Metadata (NACRS). We will also address this through a sub-study of smartphone-assisted PST.

The secondary outcome measures will include total number of suicides; representations to any Emergency Department in Ontario for the repetition of self-harm; representations to any Emergency Department in Ontario for any reason; other health system use including use of primary care and hospital outpatient appointments; mortality not related to suicide; and, health system costs within one year which will inform an economic analysis. All outcomes will be identified and measured using routinely collected data housed at ICES. Men who present with intentional self-harm in the study Emergency Departments will be identified from ICES administrative health data.

	Justification	Data Source	Data Collection Period
Primary Outcome Va	riable (composite outco	ome variable)	
Death by Suicide	To assess the clinical	ORGD, NACRS	Baseline; 12 months
and/or re-	impact of the	(ICES)	
presentation to any	provision of a		
Emergency	smartphone-assisted		
Department in	PST service.		
Ontario for Self-harm			
Secondary Outcomes	Secondary Outcomes		
Death by Suicide	To assess the clinical	ORGD (ICES)	Baseline; 12 months
	impact of the		
	provision of a		
	smartphone-assisted		
	PST service.		

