4.1.5. Sample Size

Power calculations for this trial were carried out within the logistical and practical constraints of the trial; in particular, a maximum of 25 sites are available for randomization, whereas the intervention can be implemented at only 10 sites. Consistent with previous clinical trials, we would consider a minimum relative reduction of 50% in the repetition rate to be both clinically important and achievable [47-49]. To conduct an accurate power calculation, we obtained data from ICES regarding the number of presentations with selfharm by men and the re-presentation rate to every hospital in Ontario from 2012 to 2014. Using these data, we calculated an anticipated baseline repetition rate (primary outcome) after 12 months of 13%. We also calculated an intracluster correlation coefficient (ICC) of 0.01 and an inter-period correlation of 0.008 (to account for over time correlations between pre- and post-intervention measures of the primary outcome). Given an average cluster size of 80 men and a coefficient of variation of cluster sizes (to account for imbalances in sizes) of 30%, 10 intervention clusters and 15 control clusters (2000 men) achieve 90% power to detect the minimum important difference. With 80% power, the detectable difference is a relative reduction of 41%, i.e., from a control arm rate of 13% to an intervention arm rate of 7.7% (an absolute reduction of 5.3%).

> Study Protocol Version 1, Date: December 1, 2017 Page 20 of 51

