T65812A, T65812D, T65812SToxic effect of latex, intentional self-harm.T65822A, T65822D, T65822SToxic effect of harmful algae and algae toxins, intentional self-harm.T65832A, T65832D, T65832SToxic effect of fiberglass, intentional self-harm.	T656X2A, T656X2D, T656X2S	Toxic effect of paints and dyes, not elsewhere classified, intentional self-harm.
T65822A, T65822D, T65822SToxic effect of harmful algae and algae toxins, intentional self- harm.T65832A, T65832D, T65832SToxic effect of fiberglass, intentional self-harm.	T65812A, T65812D, T65812S	Toxic effect of latex, intentional self-harm.
T65832A, T65832D, T65832SToxic effect of fiberglass, intentional self-harm.	T65822A, T65822D, T65822S	Toxic effect of harmful algae and algae toxins, intentional self- harm.
	T65832A, T65832D, T65832S	Toxic effect of fiberglass, intentional self-harm.

Toxic Effects	
T65892A, T65892D, T65892S	Toxic effect of other specified substances, intentional self-harm.
T6592XA, T6592XD, T6592XS	Toxic effect of unspecified substance, intentional self-harm.

Asphyxiation:	
T71112A, T71112D, T71112S	Asphyxiation due to smothering under pillow, intentional self-
	harm.
T71122A, T71122D, T71122S	Asphyxiation due to plastic bag, intentional self-harm.
T71132A, T71132D, T71132S	Asphyxiation due to being trapped in bed linens, intentional
	self-harm.
T71152A, T71152D, T71152S	Asphyxiation due to smothering in furniture, intentional self-
	harm.
T71162A, T71162D, T71162S	Asphyxiation due to hanging, intentional self-harm.
T71192A, T71192D, T71192S	Asphyxiation due to mechanical threat to breathing due to other
	causes, intentional self-harm.
T71222A, T71222D, T71222S	Asphyxiation due to being trapped in a car trunk, intentional
	self-harm.
T71232A, T71232D, T71232S	Asphyxiation due to being trapped in a (discarded) refrigerator,
	intentional self-harm.

* Note: Please note that all codes end in either A, D or S. These codes refer to (A) Initial Encounter, (D) Subsequent Encounter, or (S) Sequela.

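### The code list that measures self-harm re-presentation includes subsequent-encounter (D) and sequela (S) codes, so return visits for the index act could count as repeat self-harm

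*Protocol*

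**What the plan says.** Section 4.1.4 of the protocol defines the primary outcome as suicide and/or re-presentation for self-harm to any Ontario emergency department in the year after the index episode. It says that these events "will be measured using ICD-10-CM codes T360-T50992, T510-T6592, T71112-T71232, X71-X83 (refer to Appendix A for full list of codes and descriptors").

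Appendix A is the list of study sites. The self-harm codes are in section 6.2, Appendix B, where the codes are set out with endings A, D and S. The closing note reads "Please note that all codes end in either A, D or S" and continues "These codes refer to (A) Initial Encounter, (D) Subsequent Encounter, or (S) Sequela".

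The hypothesis in 3.3.1 is "Fewer contacts with the Emergency Departments in Ontario for the repetition of self-harm", and 3.3.2 has "Fewer contacts with any Emergency Departments in Ontario for the repetition of self-harm". The secondary outcomes in 4.1.4 include "representations to any Emergency Department in Ontario for the repetition of self-harm". Section 4.1.5 treats repetition and the primary outcome as the same quantity: "we calculated an anticipated baseline repetition rate (primary outcome) after 12 months of 13" percent.

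For the index episode, 4.1.2 says: "This will be identified using ICD-10-CM codes T14.91, X71-X83 ICD-10 codes from health administrative databases held at ICES".

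**The concern.** By the protocol's own labels, a D code marks a subsequent encounter and an S code marks a sequela. A man who returns because of the act that brought him into the cohort, and who is coded that way, has not repeated self-harm. Yet his visit falls within the listed codes and within the year, so under 4.1.4 he becomes a primary-outcome event.

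Visits of this kind would not be expected to fall in proportion to true repetition. If they occur equally often in both arms, they add a similar amount to each rate and pull the relative reduction towards zero. Section 4.3.3 names the relative difference as one of the two effect measures to be reported, and 4.1.5 states the minimum important effect as a 50% relative reduction.

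**Working it through.** **Step 1: is Appendix B the list meant?** The ranges in 4.1.4 match its blocks: poisoning T360X2 to T50992, toxic effects T510X2 to T6592X, asphyxiation T71112 to T71232, and self-injury X71 to X83. The reference to Appendix A is a slip.

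**Step 2: does any text remove D or S codes?** None does in 4.1.2, 4.1.4, 4.3.3 or Appendix B.

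**Step 3: the plan's own figures (4.1.5).**
- Sample size: 25 × 80 = 2,000 men.
- A 50% reduction from 13% gives 6.5%. A 41% reduction gives 0.59 × 13% = 7.7%.
- Power check: normal approximation for two proportions, 800 against 1,200 men, two-sided 5% level (assumed; the protocol states none), post-period comparison, design effect 1 + ((1 + 0.3²) × 80 − 1) × 0.01 = 1.862.
- Power for 13% against 7.7% is 79.2% (pooled variance) to 81.9% (unpooled), against the stated 80%. For 13% against 6.5% it is 94.0% to 95.5%, so the stated 90% is met.

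**Step 4: dilution.** Let p be the true 12-month event rate. Let x be the share of otherwise event-free men, equal in both arms, whose only self-harm-coded return visit is D or S. Then:

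observed rate = p + (1 − p)x, and observed absolute difference = (1 − x) × true difference.

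The protocol does not give x. The values 1% and 2% are illustrations, not estimates or bounds; x = 0 if no suffix is recorded. Nor does the protocol say whether its 13% already contains such visits, so both cases are shown.

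*Case A, the 13% contains them.* True control rate = (0.13 − x)/(1 − x); observed relative reduction = true reduction × (1 − x/0.13).

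*Case B, the 13% excludes them.* Observed control rate = 0.13 + 0.87x; observed relative reduction = true reduction × 0.13(1 − x)/(0.13 + 0.87x).

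| | x = 0 | x = 1% | x = 2% |
|---|---|---|---|
| A: true control rate | 13.0% | 12.1% | 11.2% |
| A: observed rates, true 50% reduction | 13.0% v 6.5% | 13.0% v 7.0% | 13.0% v 7.5% |
| A: a true 50% appears as | 50% | 46.2% | 42.3% |
| A: a true 41% appears as | 41% | 37.8% | 34.7% |
| B: observed rates, true 50% reduction | 13.0% v 6.5% | 13.9% v 7.4% | 14.7% v 8.4% |
| B: a true 50% appears as | 50% | 46.4% | 43.2% |
| B: a true 41% appears as | 41% | 38.0% | 35.4% |

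Worked entry (A, x = 2%): true control rate 0.11/0.98 = 0.1122, halved to 0.0561. Observed intervention rate 0.0561 + 0.9439 × 0.02 = 0.0750, and 1 − 0.0750/0.13 = 42.3%.

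In case A, the share of control-arm events that are not repeats is (1 − p)x/0.13, with p the true control rate: 6.8% at x = 1% and 13.7% at x = 2%.

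The absolute difference changes little. In case B it moves from 6.50 points to 6.44 and 6.37.

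**The case against.** The strongest reply is that no miscounting has been demonstrated. The ranges in 4.1.2 and 4.1.4 carry no suffix, 4.1.2 uses both ICD-10-CM and ICD-10 in one sentence, and the suffixes appear only in an appendix headed as codes included in collection. If the records hold no suffix, the effect is nil. This stands as a limit on size. It does not remove the point, because 4.1.4 makes the appendix list part of how the outcome is measured, and the note says that all codes carry a suffix.

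A second reply is that the primary-outcome sentence speaks of re-presentation for self-harm, and that the phrase "representations to any Emergency Department in Ontario for the repetition of self-harm" comes from the list of secondary outcomes. That is correct. But the primary hypothesis in 3.3.1 speaks of repetition, and 4.1.5 calls the repetition rate the primary outcome.

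A third reply is that code handling belongs in the statistical analysis plan. That holds for a general rule separating a new episode from continuing care, such as a clean period after the index visit. Its absence is not a finding here. The D and S codes differ, because the protocol positively lists them.

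Three stronger readings are tempting and are not supported:
- **Bias between arms.** Section 4.1.4 warns that the intervention may change help-seeking, but nothing in the protocol shows that D- or S-coded visits would differ by arm.
- **Wrong power figures.** Dilution would lower power for a given true effect on repetition, but x is unknown and no stated power is shown to be wrong.
- **The 41% as a threshold.** A reader might set a diluted 50% against the 41% detectable with 80% power. That 41% belongs to a 13% control rate. In case B the control rate rises and the detectable relative reduction falls, so the comparison misleads.

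**Conclusion.** The point holds as a conflict between the listed codes and the stated hypothesis. As written, and where the emergency department records carry the suffix, follow-up care for the index act counts as repeat self-harm.

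Its size cannot be derived from the protocol. With equal frequency in both arms and an assumed 1% or 2% of otherwise event-free men affected, a true 50% relative reduction would appear as about 46% or 42–43%, while the absolute difference scales only by (1 − x). With no suffix recorded, the effect is zero. The point deserves correction because it concerns the primary outcome and the remedy is small.

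**What to change.** In 4.1.4 and Appendix B, exclude from the self-harm re-presentation outcome any visit whose only self-harm code ends in D or S, and keep such visits under re-presentation for any reason. Apply the same restriction to index identification in 4.1.2. Correct the reference in 4.1.4 from Appendix A to Appendix B. Confirm that the 13% rate and the ICC of 0.01 were obtained on the same definition. If the ICES records carry no suffix, list the codes in the form in which they are recorded.

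The cost is a few sentences and, if the definitions differ, a re-run of the baseline query. There are two downsides. A true repeat miscoded as D or S would be missed. If the 13% included such visits, the planning rate would also fall somewhat: to 12.1% or 11.2% at the assumed 1% or 2%, and not at all if x is zero.

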6.3. List of Substance Abuse ICD-10-CM Codes Included in Data Collection

Code	Description
Alcohol:	
F1010	Alcohol abuse, uncomplicated.
F10120	Alcohol abuse with intoxication, uncomplicated.
F10121	Alcohol abuse with intoxication delirium.
F10129	Alcohol abuse with intoxication, unspecified.
F1014	Alcohol abuse with alcohol-induced mood disorder.
F10150	Alcohol abuse with alcohol-induced psychotic disorder with
	delusions.
F10151	Alcohol abuse with alcohol-induced psychotic disorder with
1 10131	hallucinations.
F10159	Alcohol abuse with alcohol-induced psychotic disorder,
	unspecified.
Alcohol:	
F10180	Alcohol abuse with alcohol-induced anxiety disorder.
F10181	Alcohol abuse with alcohol-induced sexual dysfunction.
F10182	Alcohol abuse with alcohol-induced sleep disorder.
F10188	Alcohol abuse with other alcohol-induced disorder
F1019	Alcohol abuse with unspecified alcohol-induced disorder.

Opioids:	
F1110	Opioid abuse, uncomplicated.
F11120	Opioid abuse with intoxication, uncomplicated.
F11121	Opioid abuse with intoxication delirium.
F11122	Opioid abuse with intoxication with perceptual disturbance.

F11129	Opioid abuse with intoxication, unspecified.
F1114	Opioid abuse with opioid-induced mood disorder.
E11150	Opioid abuse with opioid-induced psychotic disorder with
F11150	delusions.
E11151	Opioid abuse with opioid-induced psychotic disorder with
111131	hallucinations.
F11150	Opioid abuse with opioid-induced psychotic disorder,
111137	unspecified.
F11181	Opioid abuse with opioid-induced sexual dysfunction.
F11182	Opioid abuse with opioid-induced sleep disorder.
F11188	Opioid abuse with other opioid-induced disorder.
F1119	Opioid abuse with unspecified opioid-induced disorder.
Cannabis:	
F12120	Cannabis abuse with intoxication, uncomplicated.
F12121	Cannabis abuse with intoxication delirium.
F12122	Cannabis abuse with intoxication with perceptual disturbance.
F12129	Cannabis abuse with intoxication, unspecified.
F12150	Cannabis abuse with psychotic disorder with delusions.
F12151	Cannabis abuse with psychotic disorder with hallucinations.
F12159	Cannabis abuse with psychotic disorder, unspecified.
F12180	Cannabis abuse with cannabis-induced anxiety disorder.
F12188	Cannabis abuse with other cannabis-induced disorder.
F1219	Cannabis abuse with unspecified cannabis-induced disorder.
C. J. C.	
Sedatives:	Sodativo humantio an anvialatio abuse un complicated
Sedatives: F1310	Sedative, hypnotic or anxiolytic abuse, uncomplicated.
Sedatives: F1310 F13120	Sedative, hypnotic or anxiolytic abuse, uncomplicated. Sedative, hypnotic or anxiolytic abuse with intoxication, uncomplicated
Sedatives: F1310 F13120	Sedative, hypnotic or anxiolytic abuse, uncomplicated. Sedative, hypnotic or anxiolytic abuse with intoxication, uncomplicated. Sedative, hypnotic or anxiolytic abuse with intoxication
Sedatives: F1310 F13120 F13121	Sedative, hypnotic or anxiolytic abuse, uncomplicated. Sedative, hypnotic or anxiolytic abuse with intoxication, uncomplicated. Sedative, hypnotic or anxiolytic abuse with intoxication delirium
Sedatives: F1310 F13120 F13121	Sedative, hypnotic or anxiolytic abuse, uncomplicated. Sedative, hypnotic or anxiolytic abuse with intoxication, uncomplicated. Sedative, hypnotic or anxiolytic abuse with intoxication delirium. Sedative, hypnotic or anxiolytic abuse with intoxication
Sedatives: F1310 F13120 F13121 F13129	Sedative, hypnotic or anxiolytic abuse, uncomplicated. Sedative, hypnotic or anxiolytic abuse with intoxication, uncomplicated. Sedative, hypnotic or anxiolytic abuse with intoxication delirium. Sedative, hypnotic or anxiolytic abuse with intoxication, unspecified.
Sedatives: F1310 F13120 F13121 F13129	Sedative, hypnotic or anxiolytic abuse, uncomplicated. Sedative, hypnotic or anxiolytic abuse with intoxication, uncomplicated. Sedative, hypnotic or anxiolytic abuse with intoxication delirium. Sedative, hypnotic or anxiolytic abuse with intoxication, unspecified. Sedative, hypnotic or anxiolytic abuse with intoxication, unspecified.
Sedatives: F1310 F13120 F13121 F13129 F1314	Sedative, hypnotic or anxiolytic abuse, uncomplicated. Sedative, hypnotic or anxiolytic abuse with intoxication, uncomplicated. Sedative, hypnotic or anxiolytic abuse with intoxication delirium. Sedative, hypnotic or anxiolytic abuse with intoxication, unspecified. Sedative, hypnotic or anxiolytic abuse with sedative wi
Sedatives: F1310 F13120 F13121 F13129 F1314	Sedative, hypnotic or anxiolytic abuse, uncomplicated. Sedative, hypnotic or anxiolytic abuse with intoxication, uncomplicated. Sedative, hypnotic or anxiolytic abuse with intoxication delirium. Sedative, hypnotic or anxiolytic abuse with intoxication, unspecified. Sedative, hypnotic or anxiolytic abuse with sedative, hypnotic Sedative, hypnotic or anxiolytic abuse with sedative, hypnotic Sedative, hypnotic or anxiolytic abuse with sedative, hypnotic
Sedatives: F1310 F13120 F13121 F13129 F1314 F13150	Sedative, hypnotic or anxiolytic abuse, uncomplicated. Sedative, hypnotic or anxiolytic abuse with intoxication, uncomplicated. Sedative, hypnotic or anxiolytic abuse with intoxication delirium. Sedative, hypnotic or anxiolytic abuse with intoxication, unspecified. Sedative, hypnotic or anxiolytic abuse with sedative, hypnotic or anxiolytic abuse with sedative, hypnotic or anxiolytic abuse with sedative, hypnotic or anxiolytic-induced mood disorder. Sedative, hypnotic or anxiolytic abuse with sedative, hypnotic or anxiolytic-induced mood disorder. Sedative, hypnotic or anxiolytic abuse with sedative, hypnotic or anxiolytic-induced mood disorder.
Sedatives: F1310 F13120 F13121 F13129 F1314 F13150 F13151	Sedative, hypnotic or anxiolytic abuse, uncomplicated. Sedative, hypnotic or anxiolytic abuse with intoxication, uncomplicated. Sedative, hypnotic or anxiolytic abuse with intoxication delirium. Sedative, hypnotic or anxiolytic abuse with intoxication, unspecified. Sedative, hypnotic or anxiolytic abuse with sedative, hypnotic or anxiolytic abuse with sedative, hypnotic or anxiolytic abuse with sedative, hypnotic or anxiolytic-induced mood disorder. Sedative, hypnotic or anxiolytic abuse with sedative, hypnotic or anxiolytic-induced psychotic disorder with delusions. Sedative, hypnotic or anxiolytic abuse with sedative, hypnotic
Sedatives: F1310 F13120 F13121 F13129 F1314 F13150 F13151	Sedative, hypnotic or anxiolytic abuse, uncomplicated. Sedative, hypnotic or anxiolytic abuse with intoxication, uncomplicated. Sedative, hypnotic or anxiolytic abuse with intoxication delirium. Sedative, hypnotic or anxiolytic abuse with intoxication, unspecified. Sedative, hypnotic or anxiolytic abuse with sedative, hypnotic or anxiolytic abuse with sedative, hypnotic or anxiolytic abuse with sedative, hypnotic or anxiolytic-induced mood disorder. Sedative, hypnotic or anxiolytic abuse with sedative, hypnotic or anxiolytic-induced psychotic disorder with delusions. Sedative, hypnotic or anxiolytic abuse with sedative, hypnotic or anxiolytic-induced psychotic disorder with delusions. Sedative, hypnotic or anxiolytic abuse with sedative, hypnotic or anxiolytic-induced psychotic disorder with delusions.
Sedatives: F1310 F13120 F13121 F13129 F1314 F13150 F13151 F13159	Sedative, hypnotic or anxiolytic abuse, uncomplicated. Sedative, hypnotic or anxiolytic abuse with intoxication, uncomplicated. Sedative, hypnotic or anxiolytic abuse with intoxication delirium. Sedative, hypnotic or anxiolytic abuse with intoxication, unspecified. Sedative, hypnotic or anxiolytic abuse with sedative, hypnotic or anxiolytic abuse with sedative, hypnotic or anxiolytic abuse with sedative, hypnotic or anxiolytic-induced mood disorder. Sedative, hypnotic or anxiolytic abuse with sedative, hypnotic or anxiolytic-induced psychotic disorder with delusions. Sedative, hypnotic or anxiolytic abuse with sedative, hypnotic or anxiolytic-induced psychotic disorder with hallucinations. Sedative, hypnotic or anxiolytic abuse with sedative, hypnotic
Sedatives: F1310 F13120 F13121 F13129 F1314 F13150 F13151 F13159	Sedative, hypnotic or anxiolytic abuse, uncomplicated. Sedative, hypnotic or anxiolytic abuse with intoxication, uncomplicated. Sedative, hypnotic or anxiolytic abuse with intoxication delirium. Sedative, hypnotic or anxiolytic abuse with intoxication, unspecified. Sedative, hypnotic or anxiolytic abuse with sedative, hypnotic or anxiolytic abuse with sedative, hypnotic or anxiolytic abuse with sedative, hypnotic or anxiolytic-induced mood disorder. Sedative, hypnotic or anxiolytic abuse with sedative, hypnotic or anxiolytic-induced psychotic disorder with delusions. Sedative, hypnotic or anxiolytic abuse with sedative, hypnotic or anxiolytic-induced psychotic disorder with delusions. Sedative, hypnotic or anxiolytic abuse with sedative, hypnotic or anxiolytic-induced psychotic disorder with hallucinations. Sedative hypnotic or anxiolytic abuse with sedative, hypnotic or anxiolytic-induced psychotic disorder with hallucinations. Sedative hypnotic or anxiolytic abuse with sedative, hypnotic or anxiolytic-induced psychotic disorder, unspecified.
Sedatives: F1310 F13120 F13121 F13121 F13129 F1314 F13150 F13151 F13159 F13180	Sedative, hypnotic or anxiolytic abuse, uncomplicated.Sedative, hypnotic or anxiolytic abuse with intoxication, uncomplicated.Sedative, hypnotic or anxiolytic abuse with intoxication delirium.Sedative, hypnotic or anxiolytic abuse with intoxication, unspecified.Sedative, hypnotic or anxiolytic abuse with sedative, hypnotic
Sedatives: F1310 F13120 F13121 F13129 F1314 F13150 F13151 F13159 F13180	Sedative, hypnotic or anxiolytic abuse, uncomplicated. Sedative, hypnotic or anxiolytic abuse with intoxication, uncomplicated. Sedative, hypnotic or anxiolytic abuse with intoxication delirium. Sedative, hypnotic or anxiolytic abuse with intoxication, unspecified. Sedative, hypnotic or anxiolytic abuse with sedative, hypnotic or anxiolytic abuse with sedative, hypnotic or anxiolytic abuse with sedative, hypnotic or anxiolytic-induced mood disorder. Sedative, hypnotic or anxiolytic abuse with sedative, hypnotic or anxiolytic-induced psychotic disorder with delusions. Sedative, hypnotic or anxiolytic abuse with sedative, hypnotic or anxiolytic-induced psychotic disorder with hallucinations. Sedative hypnotic or anxiolytic abuse with sedative, hypnotic or anxiolytic abuse with sedative, hypnotic or anxiolytic-induced psychotic disorder with hallucinations. Sedative hypnotic or anxiolytic abuse with sedative, hypnotic or anxiolytic-induced psychotic disorder, unspecified. Sedative, hypnotic or anxiolytic abuse with sedative, hypnotic or anxiolytic-induced psychotic disorder, unspecified. Sedative, hypnotic or anxiolytic abuse with sedative, hypnotic or anxiolytic-induced anxiety disorder.
Sedatives: F1310 F13120 F13121 F13121 F13129 F1314 F13150 F13151 F13159 F13180 F13181	Sedative, hypnotic or anxiolytic abuse, uncomplicated.Sedative, hypnotic or anxiolytic abuse with intoxication, uncomplicated.Sedative, hypnotic or anxiolytic abuse with intoxication delirium.Sedative, hypnotic or anxiolytic abuse with intoxication, unspecified.Sedative, hypnotic or anxiolytic abuse with sedative, hypnotic or anxiolytic-induced mood disorder.Sedative, hypnotic or anxiolytic abuse with sedative, hypnotic or anxiolytic-induced mood disorder.Sedative, hypnotic or anxiolytic abuse with sedative, hypnotic or anxiolytic-induced psychotic disorder with delusions.Sedative, hypnotic or anxiolytic abuse with sedative, hypnotic or anxiolytic-induced psychotic disorder with hallucinations.Sedative, hypnotic or anxiolytic abuse with sedative, hypnotic or anxiolytic-induced psychotic disorder with hallucinations.Sedative, hypnotic or anxiolytic abuse with sedative, hypnotic or anxiolytic-induced psychotic disorder, unspecified.Sedative, hypnotic or anxiolytic abuse with sedative, hypnotic or anxiolytic-induced psychotic disorder, unspecified.Sedative, hypnotic or anxiolytic abuse with sedative, hypnotic or anxiolytic-induced anxiety disorder.Sedative, hypnotic or anxiolytic abuse with sedative, hypnotic or anxiolytic-induced anxiety disorder.
Sedatives: F1310 F13120 F13121 F13121 F13129 F1314 F13150 F13151 F13159 F13181	Sedative, hypnotic or anxiolytic abuse, uncomplicated.Sedative, hypnotic or anxiolytic abuse with intoxication, uncomplicated.Sedative, hypnotic or anxiolytic abuse with intoxication delirium.Sedative, hypnotic or anxiolytic abuse with intoxication, unspecified.Sedative, hypnotic or anxiolytic abuse with sedative, hypnotic or anxiolytic-induced mood disorder.Sedative, hypnotic or anxiolytic abuse with sedative, hypnotic or anxiolytic-induced psychotic disorder with delusions.Sedative, hypnotic or anxiolytic abuse with sedative, hypnotic or anxiolytic-induced psychotic disorder with delusions.Sedative, hypnotic or anxiolytic abuse with sedative, hypnotic or anxiolytic-induced psychotic disorder with hallucinations.Sedative, hypnotic or anxiolytic abuse with sedative, hypnotic or anxiolytic-induced psychotic disorder with hallucinations.Sedative, hypnotic or anxiolytic abuse with sedative, hypnotic or anxiolytic-induced psychotic disorder, unspecified.Sedative, hypnotic or anxiolytic abuse with sedative, hypnotic or anxiolytic-induced anxiety disorder.Sedative, hypnotic or anxiolytic abuse with sedative, hypnotic or anxiolytic-induced sexual dysfunction.Sedative, hypnotic or anxiolytic abuse with sedative, hypnotic or anxiolytic-induced sexual dysfunction.
Sedatives: F1310 F13120 F13121 F13129 F13129 F1314 F13150 F13151 F13159 F13180 F13182	Sedative, hypnotic or anxiolytic abuse, uncomplicated.Sedative, hypnotic or anxiolytic abuse with intoxication, uncomplicated.Sedative, hypnotic or anxiolytic abuse with intoxication delirium.Sedative, hypnotic or anxiolytic abuse with intoxication, unspecified.Sedative, hypnotic or anxiolytic abuse with sedative, hypnotic or anxiolytic-induced mood disorder.Sedative, hypnotic or anxiolytic abuse with sedative, hypnotic or anxiolytic-induced psychotic disorder with delusions.Sedative, hypnotic or anxiolytic abuse with sedative, hypnotic or anxiolytic-induced psychotic disorder with hallucinations.Sedative hypnotic or anxiolytic abuse with sedative, hypnotic or anxiolytic-induced psychotic disorder with hallucinations.Sedative hypnotic or anxiolytic abuse with sedative, hypnotic or anxiolytic-induced psychotic disorder, unspecified.Sedative hypnotic or anxiolytic abuse with sedative, hypnotic or anxiolytic-induced psychotic disorder, unspecified.Sedative, hypnotic or anxiolytic abuse with sedative, hypnotic or anxiolytic-induced anxiety disorder.Sedative, hypnotic or anxiolytic abuse with sedative, hypnotic or anxiolytic-induced anxiety disorder.Sedative, hypnotic or anxiolytic abuse with sedative, hypnotic or anxiolytic-induced sexual dysfunction.Sedative, hypnotic or anxiolytic abuse with sedative, hypnotic or anxiolytic-induced sexual dysfunction.
Sedatives: F1310 F13120 F13121 F13121 F13129 F1314 F13150 F13151 F13159 F13180 F13182	Sedative, hypnotic or anxiolytic abuse, uncomplicated. Sedative, hypnotic or anxiolytic abuse with intoxication, uncomplicated. Sedative, hypnotic or anxiolytic abuse with intoxication delirium. Sedative, hypnotic or anxiolytic abuse with intoxication, unspecified. Sedative, hypnotic or anxiolytic abuse with sedative, hypnotic or anxiolytic-induced mood disorder. Sedative, hypnotic or anxiolytic abuse with sedative, hypnotic or anxiolytic-induced psychotic disorder with delusions. Sedative, hypnotic or anxiolytic abuse with sedative, hypnotic or anxiolytic-induced psychotic disorder with hallucinations. Sedative hypnotic or anxiolytic abuse with sedative, hypnotic or anxiolytic-induced psychotic disorder with hallucinations. Sedative hypnotic or anxiolytic abuse with sedative, hypnotic or anxiolytic-induced psychotic disorder, unspecified. Sedative hypnotic or anxiolytic abuse with sedative, hypnotic or anxiolytic-induced anxiety disorder. Sedative, hypnotic or anxiolytic abuse with sedative, hypnotic or anxiolytic-induced sexual dysfunction. Sedative, hypnotic or anxiolytic abuse with sedative, hypnotic or anxiolytic-induced sexual dysfunction. Sedative, hypnotic or anxiolytic abuse with sedative, hypnotic or anxiolytic-induced sexual dysfunction. Sedative, hypnotic or anxiolytic abuse with sedative, hypnotic or anxiolytic-induced sexual dysfunction. Sedative, hypnotic or anxiolytic abuse with sedative, hypnotic or anxiolytic-induced sexual dysfunction.
Sedatives: F1310 F13120 F13121 F13121 F13129 F1314 F13150 F13151 F13159 F13180 F13182 F13188	Sedative, hypnotic or anxiolytic abuse, uncomplicated.Sedative, hypnotic or anxiolytic abuse with intoxication, uncomplicated.Sedative, hypnotic or anxiolytic abuse with intoxication delirium.Sedative, hypnotic or anxiolytic abuse with intoxication, unspecified.Sedative, hypnotic or anxiolytic abuse with sedative, hypnotic or anxiolytic-induced mood disorder.Sedative, hypnotic or anxiolytic abuse with sedative, hypnotic or anxiolytic-induced mood disorder with delusions.Sedative, hypnotic or anxiolytic abuse with sedative, hypnotic or anxiolytic-induced psychotic disorder with delusions.Sedative, hypnotic or anxiolytic abuse with sedative, hypnotic or anxiolytic-induced psychotic disorder with hallucinations.Sedative, hypnotic or anxiolytic abuse with sedative, hypnotic or anxiolytic-induced psychotic disorder, unspecified.Sedative, hypnotic or anxiolytic abuse with sedative, hypnotic or anxiolytic-induced psychotic disorder, unspecified.Sedative, hypnotic or anxiolytic abuse with sedative, hypnotic or anxiolytic-induced anxiety disorder.Sedative, hypnotic or anxiolytic abuse with sedative, hypnotic or anxiolytic-induced sexual dysfunction.Sedative, hypnotic or anxiolytic abuse with sedative, hypnotic or anxiolytic-induced sexual dysfunction.Sedative, hypnotic or anxiolytic abuse with sedative, hypnotic or anxiolytic-induced secual dysfunction.Sedative, hypnotic or anxiolytic abuse with other sedative, hypnotic or anxiolytic abuse with other sedative, hypnotic or anxiolytic induced sleep disorder.
Sedatives: F1310 F13120 F13121 F13129 F13129 F1314 F13150 F13151 F13159 F13180 F13182 F13188	Sedative, hypnotic or anxiolytic abuse, uncomplicated. Sedative, hypnotic or anxiolytic abuse with intoxication, uncomplicated. Sedative, hypnotic or anxiolytic abuse with intoxication delirium. Sedative, hypnotic or anxiolytic abuse with intoxication, unspecified. Sedative, hypnotic or anxiolytic abuse with sedative, hypnotic or anxiolytic-induced mood disorder. Sedative, hypnotic or anxiolytic abuse with sedative, hypnotic or anxiolytic-induced psychotic disorder with delusions. Sedative, hypnotic or anxiolytic abuse with sedative, hypnotic or anxiolytic-induced psychotic disorder with hallucinations. Sedative, hypnotic or anxiolytic abuse with sedative, hypnotic or anxiolytic-induced psychotic disorder with hallucinations. Sedative, hypnotic or anxiolytic abuse with sedative, hypnotic or anxiolytic-induced psychotic disorder, unspecified. Sedative, hypnotic or anxiolytic abuse with sedative, hypnotic or anxiolytic-induced anxiety disorder. Sedative, hypnotic or anxiolytic abuse with sedative, hypnotic or anxiolytic-induced sexual dysfunction. Sedative, hypnotic or anxiolytic abuse with sedative, hypnotic or anxiolytic-induced sexual dysfunction. Sedative, hypnotic or anxiolytic abuse with sedative, hypnotic or anxiolytic-induced sleep disorder. Sedative, hypnotic or anxiolytic abuse with other sedative, hypnotic or anxiolytic-induced disorder. Sedative, hypnotic or anxiolytic abuse with other sedative, hypnotic or anxiolytic-induced disorder.

Study Protocol Version 1, Date: December 1, 2017 Page 44 of 51

Stimulants:	
F1410	Cocaine abuse, uncomplicated.
F14120	Cocaine abuse with intoxication, uncomplicated.
F14121	Cocaine abuse with intoxication with delirium.
F14122	Cocaine abuse with intoxication with perceptual disturbance.
F14129	Cocaine abuse with intoxication, unspecified.
F1414	Cocaine abuse with cocaine-induced mood disorder.
E14150	Cocaine abuse with cocaine-induced psychotic disorder with
F14150	delusions.
E14151	Cocaine abuse with cocaine-induced psychotic disorder with
F14151	hallucinations.
E14150	Cocaine abuse with cocaine-induced psychotic disorder,
F14139	unspecified.
F14180	Cocaine abuse with cocaine-induced anxiety disorder.
F14181	Cocaine abuse with cocaine-induced sexual dysfunction.
F14182	Cocaine abuse with cocaine-induced sleep disorder.
F14188	Cocaine abuse with other cocaine-induced disorder.
